FAST in hemodynamically unstable trauma patients. We plan to prospectively collect data for creation of a multicenter database; enrolled subjects would undergo both the standard FAST and when appropriate (see Methods) a FASTeR. Our aim is to determine the sensitivity and specificity of the FAST and FASTeR, and determine which exam was more accurate in recognizing hemoperitoneum. Exam results will be confirmed with computed tomography (CT) imaging or operative findings.

Potential Risks and Benefits

Potential Risks

There are no expected medical risks to the study participants in excess of the normal risks of the FAST, which is minimal.

Potential Benefits

If the FASTeR is shown to detect small volumes of hemoperitoneum earlier than was previously possible with the FAST, patients may directly benefit from earlier diagnosis and treatment. Early identification of hemoperitoneum has been shown to be strongly correlated with increased survival rates (1).

Study Objectives

Primary Objective

To calculate and compare the sensitivity and specificity of detecting hemoperitoneum in the RUQ for the standard FAST and the FASTeR in the research subjects. Actual injury complex will be confirmed by CT or operative findings.

Secondary Objective

To calculate and compare the false positive rate, false negative rate, positive predictive value, negative predictive value, and positive and negative likelihood ratios for the standard FAST and FASTeR. Exam results for individual subjects will be compared to see if there is a significant difference in result accuracy.

Study Design

This is a prospective multicenter study. Detailed responsibilities for the lead (Memorial Regional Hospital) and satellite centers below.

Memorial Regional Hospital (lead)

- 1. Maintain database for enrolled MRH subjects. Data collected will include HIPAA identifiers (included in outcome measures) to monitor our own data integrity.
- 2. As lead center, MRH will aggregate and analyze collected data from satellite centers which will be submitted without HIPAA identifiers.
- 3. MRH to manage subjects meeting inclusion criteria according to our institutional patient management protocols.
- 4. MRH to adhere to IRB protocol and application as submitted.

Satellite Centers

- 1. Each center must apply and receive IRB approval from their respective IRB(s).
- 2. Each center is responsible for their own data integrity, as outlined in their approved IRB protocol and application.

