Patients with clinical history or physical signs suspicious for blunt abdominal trauma will undergo the standard FAST in the emergency department as per ATLS protocol. During the secondary survey, all patients are rolled for examination of their back and removal of the rigid spine board, per ATLS. In our study, we will standardize this practice so that all patients are rolled onto their right side for this portion of the examination. Patients with extensive right sided chest trauma will be excluded at the discretion of the Trauma Surgeon. After the right sided roll to remove the back board, a repeat ultrasound examination of the RUQ will be performed.

All participating centers, including MRH, will collect and submit the following data to the database for each enrolled subject: age, gender, initial trauma bay vital signs, mechanism of injury, results of the FAST, results of the FASTeR, and injury complex as confirmed by CT imaging or operative findings for their respective centers. Both the CT scan and any surgical intervention that the participant undergoes as a study subject will be performed through routine standard of care procedures. The database will not contain HIPAA identifiers

MRH will record our internal subject medical record numbers and dates of admission to verify data fields and monitor our own data integrity. All data will be de-identified prior to publication.

Study Outcome Measures (Endpoints)

The study outcome measures will be recorded using the "Multicenter Study: Can we be FASTeR? A multicenter study utilizing Right sided roll to improve sensitivity of the FAST examination" data collection form. The patient medical record number (MRN) will be

recorded by hand on the tool for all MRH enrolled subjects only; subject data will be cross-checked with the electronic records in order to maximize data integrity.

- 1. Number of patients admitted and discharged from MRH between the timeframe (October 16, 2017- October 16, 2019) who present as a trauma activation with clinical history or physical signs of blunt abdominal trauma and hemodynamic instability
 - a. MRN (recorded by hand), internal use only
 - b. Admission date (recorded by hand), internal use only
- 2. Demographics (e.g. age, gender)
- 3. Admission vital signs (e.g. heart rate [bpm], blood pressure, respiratory rate, oxygen saturation)
- 4. Results (positive or negative) of the FAST (RUQ, LUQ, surprapubic)
- 5. Results of the FASTeR (RUQ)

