- 6. Method where final injury complex determined (if applicable)
 - a. Operative findings
 - b. CT scans
 - c. Other imaging (e.g. MRI, x-ray, ultrasound)
- 7. Final injury complex (if applicable)
 - a. Liver injury
 - b. Splenic injury
 - c. Gastrointestinal injury (type)
 - d. Genitourinary injury (type)
 - e. Vascular/mesenteric injury (type)
 - f. Pancreatic injury
 - g. Other (type)
- 8. Outcome of hemoperitoneum confirmed by imaging or operative findings

Statistical Analysis Plan

All subjects who meet inclusion criteria and have complete data available will be used for data analysis. The sensitivity and specificity (with confidence intervals) for detecting hemoperitoneum using the standard FAST or the FASTeR versus the actual injury complex findings (CT or operative findings) will be calculated in the research subjects along with the false positive rate, false negative rate, positive predictive value, negative predictive value, and positive and negative likelihood ratios. A McNemar's test will be used to directly compare the accuracy of the FAST and FASTeR results for individual research subjects.

The data pooled from the participating centers will provide a robust data set that will minimize center or physician specific result bias and provide the needed statistical volume as calculated by the power analysis.

Study Procedures

Subject Identification, Recruitment, and Screening

This a prospective multicenter study, which will prospectively record data without altering the manner in which the patients are managed by the surgeon and institution. Accordingly, an informed consent waiver is requested. All data will be recorded on a data sheet and transferred to a secured database (REDCap) without patient identifiers.

Eligibility for study enrollment will be considered for all patients presenting to MRH as a trauma alert during the study period, with a clinical history or physical signs for blunt abdominal trauma who would clinically indicate a standard FAST in the trauma bay as per ATLS protocol. Patients with extensive right sided chest trauma will be excluded at the discretion of the Trauma Surgeon. Both the CT scan and any surgical intervention that the participant undergoes as a study subject will be performed through routine standard of care procedures.

Study Duration

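### Outcome-form items 6c and 8 accept imaging beyond the SAP's CT-or-operative reference, including ultrasound, and no rule covers subjects verified only that way

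*Combined protocol and SAP*

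**What the plan says.** Four statements in the combined protocol and SAP give the same reference standard:

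- Rationale: "Exam results will be confirmed with computed tomography (CT) imaging or operative findings".
- Primary Objective: "Actual injury complex will be confirmed by CT or operative findings".
- Research Design, in the list of data that centers submit: "injury complex as confirmed by CT imaging or operative findings for their respective centers".
- Statistical Analysis Plan: sensitivity and specificity are computed "versus the actual injury complex findings (CT or operative findings) will be calculated in the research subjects".

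The section Study Outcome Measures (Endpoints), which describes the data collection form, is wider in two places. Item 6, "Method where final injury complex determined (if applicable", offers operative findings (6a), CT (6b) and a third option (6c): "Other imaging (e.g. MRI, x-ray, ultrasound". Item 8, the only listed field for the target condition itself, reads "Outcome of hemoperitoneum confirmed by imaging or operative findings", with imaging not limited to CT.

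The index test is also ultrasound: under Research Design, after the roll, "a repeat ultrasound examination of the RUQ will be performed". Its result has its own field (item 5), as does FAST (item 4).

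The SAP analyses subjects who meet the inclusion criteria and have complete data. It does not define complete for the reference result. CT and surgery are done only as routine care requires.

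**The concern.** A center that follows the form as written can record hemoperitoneum as confirmed when neither CT nor operation took place, and can give ultrasound as the method. If that ultrasound is the FAST or FASTeR scan, the index test is being judged against itself. A positive scan is then correct by construction, and bleeding that the scan missed is labelled disease-free. Sensitivity, which is part of the primary objective, would be overstated.

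Such records can arise because the study mandates neither CT nor operation and each center follows its own management protocol. They would also be hard to correct later. Satellite centers send de-identified data and answer for their own data integrity; cross-checking against electronic records is described only for the lead center. Without a written rule, the handling of 6c-only subjects could be settled after results have been seen, including at the interim analyses after 100 and 200 subjects.

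**Working it through.** The plan states no figure on this point. The check is a comparison of texts, followed by an illustration of size.

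**1. Texts side by side**

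| Place | Accepted reference |
|---|---|
| Rationale; Primary Objective; Research Design; SAP | CT or operation |
| Outcome item 6 (injury complex) | operation, CT, or other imaging including ultrasound |
| Outcome item 8 (hemoperitoneum) | any imaging, or operation |

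The form contradicts the SAP. No sentence resolves the conflict or says what becomes of a 6c-only subject.

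**2. Inputs for the illustration**

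- FAST sensitivity 0.60: Study Duration gives up to 60% of subjects with significant intra-abdominal injury, taken here as sensitivity for hemoperitoneum.
- FASTeR sensitivity: FASTeR finds 1 in 4 of those FAST missed, so 0.60 + 0.25 × 0.40 = 0.70.
- Assumed: FASTeR is positive whenever FAST is.
- Assumed: a share u of true cases has FASTeR as its reference; u = 10% and 20% are illustrative.

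**3. Apparent sensitivity**

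In the share u, the 30% of true cases that FASTeR misses are relabelled negative and leave the denominator, which becomes (1 − u) + 0.70u = 1 − 0.30u. All FAST-positive and FASTeR-positive cases stay, so the numerators do not change.

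| u | FASTeR = 0.70/(1 − 0.30u) | FAST = 0.60/(1 − 0.30u) | Gap (points) |
|---|---|---|---|
| 0 | 70.0% | 60.0% | 10.0 |
| 10% | 0.70/0.97 = 72.2% | 0.60/0.97 = 61.9% | 10.3 |
| 20% | 0.70/0.94 = 74.5% | 0.60/0.94 = 63.8% | 10.6 |

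A second version takes a share f of all patients. It assumes specificity 0.97 (the background cites 94.7–99.6%), hemoperitoneum prevalence 20–40% (not in the documents) and false positives common to both tests. At f = 10% it gives FAST 0.62, FASTeR 0.72–0.73 and specificity 0.973. At f = 30% it gives 0.66–0.67, 0.77–0.78 and about 0.98. The gap is then about 11 points.

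**4. McNemar's test**

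- *True case, FASTeR positive and FAST negative.* This is a pair in FASTeR's favour under CT and under self-reference. No change.
- *True case missed by both.* Both are wrong under CT and both right under self-reference. It is concordant either way. No change.
- *No hemoperitoneum, FASTeR positive and FAST negative.* This pair favours FAST under CT and FASTeR under self-reference. It changes sides.

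Only the third type moves the test, given that FASTeR is positive whenever FAST is. As hypothetical counts, 6 against 1 gives exact two-sided p = 2 × (1 + 7)/2^7 = 0.125. If the one opposing pair changes sides, 7 against 0 gives p = 2/2^7 = 0.016.

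**The case against.** The strongest reply is that the SAP already settles the matter. It names CT or operative findings as the comparator, and three other places agree. On that reading a subject with neither has no reference result and is more naturally incomplete than complete. Item 6 records the method, so 6c-only subjects can be found and removed. FAST and FASTeR have their own fields, 6c does not name them, and item 7 spells out the injury complex as organ injuries, whereas the background describes the scans as looking for fluid. A separate later ultrasound is at least as natural a reading of 6c.

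Much of this stands. A reader might infer that the plan uses the index test as its own reference, or that 6c-only subjects count as complete data and enter the 2x2 table. The documents say neither. What remains is item 8: it is the field that records hemoperitoneum, and it accepts imaging without limit. The SAP does not say that an item 8 result resting only on 6c must be set aside. Being able to find these subjects is not a rule for handling them.

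A reader might also infer that one or two self-confirmed subjects could decide the comparison, since six FASTeR-only pairs with none opposing already give p = 2 × 0.5^6 = 0.031. That does not follow for true cases, whose pairs are the same under CT. It would take self-confirmed FASTeR-only false positives, and nothing in the documents indicates how many there would be, if any.

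**Conclusion.** The contradiction is established from the text and needs correcting. The bias is possible rather than built in: it occurs only if an index scan supplies the reference and the subject is then analysed as verified.

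If it occurs, the effect falls mainly on the absolute accuracy figures. Sensitivity would be about 2 points too high for both tests at u = 10% and about 4 points at u = 20%, and specificity would be slightly too high. The FASTeR–FAST gap would barely move. These sizes rest on the plan's projected sensitivities, on FASTeR being positive whenever FAST is, and on shares for which the documents give no basis. If some FAST-positive true cases were FASTeR-negative, using FASTeR as reference would mislabel them too, in FASTeR's favour; the illustration leaves this out.

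**What to change.** - Change item 8 so that hemoperitoneum is confirmed by CT or operative findings only.
- State in the SAP that only 6a or 6b supplies the reference, and that FAST and FASTeR never do. Item 6c may stay as a descriptive field.
- State in the SAP that subjects whose only method is 6c are unverified, are left out of the primary 2x2 and McNemar analyses, and are reported by number and by FAST and FASTeR result.

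The incorporation argument applies to ultrasound alone. Leaving MRI and x-ray out rests on agreement with the SAP's own definition.

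The cost is a reworded form field and a short SAP addition, with no change to patient care. A few subjects may leave the primary set. Excluding unverified subjects can itself cause partial-verification bias, and the SAP has no analysis for that, so their number and scan results need to be shown. The rule should be in place before the first interim analysis.

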Rapid diagnosis and management of intra-abdominal hemorrhage after blunt trauma is critical in the triage and assessment of trauma patients (1). The Focused Assessment with Sonography in Trauma examination (FAST) is an efficient, bedside, non-ionizing, non-invasive method for assessing hemoperitoneum (the presence of blood in the peritoneal cavity), in traumatically injured patients. The FAST is taught during the Acute Trauma Life Support (ATLS) Course, and is the gold standard for the initial assessment of abdominal and chest trauma (2). FASTs have excellent specificity (94.7-99.6% in most series), however sensitivity is low (20-60%) (3-5). Improving the sensitivity of the FAST would allow for earlier detection and management of life-threatening intra-abdominal hemorrhage for innumerable trauma patients.

FASTs are typically performed with the patient in the standard position, lying flat on their back. The right upper quadrant (RUQ), left upper quadrant (LUQ) and suprapubic region are scanned and evaluated for hemoperitoneum. If fluid is found in any of these views, the patient is emergently taken to the operating room (OR) to treat the intra-abdominal hemorrhage.

It has been previously shown that a standard FAST is most likely to detect hemoperitoneum in the RUQ in Morison's pouch, the space on the right side of the body that separates the liver and the right kidney (hepatorenal recess) (2). A recent pilot by Pigneri et al., compared standard FAST exam to FAST exam after the patient had been rolled onto their right side; this modified evaluation method was termed Focused Assessment with Sonography in Trauma examination after Right sided roll (FASTeR). The rationale was this position likely uses gravity to collect intra-abdominal fluid into Morison's pouch, thus making it possible to visualize small volumes of fluid that would otherwise be undetectable when the patient is lying flat (6). This study demonstrated earlier identification of intra-abdominal fluid with the FASTeR when compared to the standard FAST (6).

Rationale

All patients are rolled onto one side or the other during normal trauma evaluation. Changing practice to turn the patient onto the right side for a modified FAST, or FASTeR, can potentially increase exam sensitivity without delaying care. Our goal is to perform a large, multicenter study to evaluate the impact of FASTeR versus the standard

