- 3. Each center to provide IRB outcome or waiver letter to the lead center.
- 4. Each center to complete the data sharing agreement specific to this study.
- 5. Each center to provide care according to their institutional patient management protocols.
- 6. Each center to submit de-identified data to the lead center for analysis.

Subject Selection

Inclusion Criteria

1. Patients over 18 and under 89 years of age who present as a trauma activation with clinical history or physical signs of blunt abdominal trauma and hemodynamic instability

Exclusion Criteria

- 1. Patients under 18 and over 89 years
- 2. Pregnant women
- 3. Patients with prohibitive right sided chest trauma
- 4. Patients in extremis undergoing salvage maneuvers (chest compressions or emergent surgical intervention) which prevents performance of an ultrasound examination
- 5. Patients who leave against medical advice or are otherwise removed from the medical system before their work up has been completed

Sample Size

50 participants at MRH and 250 participants total for all sites.

Research Design

This is a prospective multicenter study, where MRH will act as the lead center. Each contributing center is responsible for obtaining IRB approval and maintaining data integrity outlined in their approved IRB protocol and application from their respective institutions. Once IRB approval has been obtained, we will begin enrolling trauma patients prospectively into a registry. The participating centers for this study represent a diverse set of trauma centers and emergency departments and include institutions with varying trauma verifications (e.g. ACS and State), sizes, geographical/metropolitan locations, and resource availability to ensure inclusivity.

Since this is a prospective observational study, data will be collected prospectively without altering the manner in which the patients are managed by the surgeon and institution. Accordingly, an informed consent waiver is requested. Patients will be given a flyer with information about the study (see additional documents). Data will be collected for a two year period with interim analysis when specific enrollment targets are met. All data will be recorded on a data sheet and transferred to a secured database (REDCap) without patient identifiers.

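### The complete-data rule can select subjects on their FAST result, and the plan does not tabulate who is lost or why

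*Combined protocol and SAP*

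**What the plan says.** The Statistical Analysis Plan restricts the analysis as follows: "All subjects who meet inclusion criteria and have complete data available will be used for data analysis". It compares the two exams with McNemar's test, which needs both results in each subject. The Primary Objective is "To calculate and compare the sensitivity and specificity of detecting hemoperitoneum in the RUQ for the standard FAST and the FASTeR", judged against CT or operative findings.

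The order and completeness of the scans are described in several places:

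- **Research Design:** FAST comes first. At the secondary survey, "we will standardize this practice so that all patients are rolled onto their right side", and the RUQ is then rescanned. The same section says that "data will be collected prospectively without altering the manner in which the patients are managed by the surgeon and institution".
- **Background (before Rationale), on usual practice:** "If fluid is found in any of these views, the patient is emergently taken to the operating room (OR".
- **Rationale:** "enrolled subjects would undergo both the standard FAST and when appropriate (see Methods) a FASTeR".
- **Exclusion Criteria:** item 4 removes "Patients in extremis undergoing salvage maneuvers (chest compressions or emergent surgical intervention) which prevents performance of an ultrasound examination", without saying which ultrasound. Item 5 removes patients who leave or are "otherwise removed from the medical system before their work up has been completed".
- **Withdrawal of Subjects:** those who cannot tolerate the roll become screening failures and are withdrawn.

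The only denominator planned is item 1 of Study Outcome Measures, a count of presenting patients at the lead center. It is not split by FAST result or by reason for loss. No missing-data method or sensitivity analysis is given.

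**The concern.** Read together, these sections leave a route by which the FAST result itself decides whether a subject is analysed. A FAST-positive subject may leave for surgery before the roll. That subject has everything needed to count towards FAST sensitivity (a FAST and an operative reference), yet lacks a FASTeR and is therefore not complete. In the other direction, CT is done only as routine care, so a FAST-negative subject may have neither CT nor operative findings and is dropped as well.

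At stake are the reported sensitivity and specificity of FAST, which are part of the primary objective, and the reported gain from FASTeR. The two kinds of loss act in opposite directions on FAST sensitivity. Without a count of each, a reader cannot tell which dominated.

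**Working it through.** **Inputs from the documents.** FAST sensitivity is up to 60%, and FASTeR finds 1 in 4 of injured subjects with a negative FAST (Study Duration). FAST specificity is 94.7%, the low end of the Background's range. The plan's implied FASTeR sensitivity is 60 + 0.25 × 40 = 70%, a gain of 10 points, if no FAST-positive subject turns negative.

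**Assumed.** L is the fraction of FAST-positives lost before FASTeR, unrelated to the unseen FASTeR result. V is the fraction of FAST-negatives without a reference. Neither is in the documents.

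**1. Loss of FAST-positives.** Per 100 subjects with hemoperitoneum, 60 are positive on both exams, 10 on FASTeR only and 30 on neither.

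- FAST sensitivity = 60(1−L)/(100−60L)
- Gain = 10/(1−0.6L) points
- FAST specificity = 94.7/(94.7 + 5.3(1−L)), applying the same loss rate to false positives

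| L | FAST sensitivity | FASTeR sensitivity | Gain (points) | FAST specificity |
|---|---|---|---|---|
| 0 | 60% | 70% | 10.0 | 94.7% |
| 10% | 54/94 = 57.4% | 64/94 = 68.1% | 10.6 | 95.2% |
| 25% | 45/85 = 52.9% | 55/85 = 64.7% | 11.8 | 96.0% |
| 50% | 30/70 = 42.9% | 40/70 = 57.1% | 14.3 | 97.3% |

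**2. Missing reference in FAST-negatives.** FAST sensitivity = 60(1−L)/(60(1−L) + 40(1−V)). With L = 0 and V = 50% it is 60/80 = 75%. With both at 50% it is 30/50 = 60%.

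**3. RUQ objective.** FAST covers three views and FASTeR only the RUQ. Let g be the gains (FASTeR positive, FAST RUQ negative) and r the reversals (FAST RUQ positive, FASTeR negative), both per 100. Let s be the share of gains already positive in another FAST view. With any-view sensitivity of 60%:

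reported gain = [g(1−sL) − r(1−L)]/(1−0.6L), against a true gain of g − r.

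Setting the two equal gives s = 0.6 + 0.4r/g. The gain is overstated below that share and understated above it.

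- g = 10, r = 0: break-even is 60%. At 50% loss the reported gain runs from 10/0.7 = 14.3 (s = 0) down to 5/0.7 = 7.1 (s = 1).
- g = 18, r = 8: break-even is 0.6 + 3.2/18 = 78%. At s = 70% and 50% loss the reported gain is (11.7 − 4)/0.7 = 11.0 against a true 10.

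**4. McNemar's test.** Simulated with 100 subjects with hemoperitoneum, counting rejections in favor of FASTeR at two-sided 5%. The plan does not say whether the test is exact or uncorrected.

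| Cells | L | Uncorrected | Exact |
|---|---|---|---|
| Plan (10 gains, 0 reversals) | 0, 25% or 50% | 99% | 94% |
| Null, 8% gains and 8% reversals | 50% | about 19% | about 13% |
| Null, 2% gains and 2% reversals | 50% | about 5% | about 0.6% |

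With no loss, the uncorrected null rates are about 2%. With no reversals, loss removes only concordant pairs, so the test does not change.

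**5. Worst-case bounds for missing FASTeR.** Counting all missing FASTeR results as negative gives 70 − 60L, and counting all as positive gives 70. The ranges are 64–70%, 55–70% and 40–70% at 10%, 25% and 50% loss. The lower end exceeds 60% only if L < 1/6.

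**The case against.** The strongest reply is that the loss is not a stated procedure. Research Design has all patients rolled to the right and rescanned, and asks for a FASTeR result on each enrolled subject. The operating-room sentence is background on usual practice. The Rationale's qualifier on FASTeR points to the methods, where right-sided chest trauma is the exception named. Exclusion 4 concerns patients in extremis, and failure to tolerate the roll need not depend on the FAST result. All of this stands. A reader might infer that the plan makes FASTeR conditional on a negative FAST, or that FAST-positives will routinely miss it. No section says so.

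The size may also be modest. At 10% to 25% loss the gain shifts by 0.6 to 1.8 points. The 95% half-width is 1.96√(0.1 × 0.9/n), about 5.9 points with 100 subjects with hemoperitoneum and 4.1 with 209. That is fair for the gain. The shift in FAST sensitivity itself is larger: 7 points at 25% loss.

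Other provisions help only in part. The lead-center count covers a site planned to supply 50 of 250 subjects. The accrual allowance of 41 (250 − 209) protects numbers and does not prevent selection. Other imaging is recorded as a way of determining injury, so a missing CT is not always a missing record, but the Statistical Analysis Plan names only CT or operative findings as the reference.

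**Conclusion.** The concern holds as a possibility that the plan leaves open and would not reveal. The complete-data rule can select on FAST, and no table would show whether it did. It should be corrected; confidence is medium, because every loss rate is assumed.

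If only FAST-positives are lost, FAST sensitivity is understated (57%, 53% or 43% against 60%) and FAST specificity is overstated (95.2%, 96.0% or 97.3% against 94.7%). The 10-point gain becomes 10.6, 11.8 or 14.3 when extra detections come only from FAST-negatives. Missing reference in FAST-negatives works against this on sensitivity.

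Two stronger conclusions are tempting and unsupported. The first is that the RUQ comparison is biased towards FASTeR. Its direction depends on the other-view share and on reversals, and the documents give neither. The second is that McNemar's test is invalid. Within hemoperitoneum it is unaffected without reversals, and the inflation with reversals depends on their frequency and on the test version. With 2% reversals and the exact test there is none above the nominal level.

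**What to change.** 1. Reconcile the Background, Rationale, Exclusion Criteria, Research Design and Withdrawal of Subjects sections on who gets a FASTeR and who is removed after FAST is read, including whether exclusion 4 covers a FASTeR missed after a completed FAST.
2. Keep the complete-case paired analysis.
3. Record every otherwise eligible subject with a FAST, including those later removed. Tabulate missing FASTeR and missing reference by FAST view result (RUQ, LUQ, suprapubic), reason and center. The view results are already collected.
4. Report FAST sensitivity and specificity in all subjects with FAST and reference beside the complete-case values. Add bounds that count unverified FAST-negatives all with, then all without, hemoperitoneum.
5. Show best-case and worst-case bounds for missing FASTeR as a sensitivity analysis only. On plan figures they keep FASTeR above 60% only when loss is below one-sixth. If loss is larger, limit the conclusion to subjects who had both scans.

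The cost is one table, modest analysis work and wider reported ranges. Keeping data on subjects now withdrawn needs a small protocol amendment at the lead and satellite IRBs. Patient care does not change.

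### Complete-case analysis against a routine-care reference standard puts the primary sensitivity and specificity at risk of partial verification bias, and no correction or sensitivity analysis is planned

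*Combined protocol and SAP*

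**What the plan says.** All references are to the combined protocol and SAP.

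- **Primary Objective:** calculate and compare the sensitivity and specificity of FAST and FASTeR for hemoperitoneum in the right upper quadrant.
- **Statistical Analysis Plan:** "All subjects who meet inclusion criteria and have complete data available will be used for data analysis". Accuracy is measured "versus the actual injury complex findings (CT or operative findings) will be calculated in the research subjects".
- **Research Design:** CT and surgery "will be performed through routine standard of care procedures". Elsewhere, this section says that "data will be collected prospectively without altering the manner in which the patients are managed by the surgeon and institution".
- **Study Outcome Measures, item 6:** "Method where final injury complex determined (if applicable"). Item 7, the injury complex itself, carries the same qualifier. Item 6 also has a line for other imaging, which the analysis section does not name as a reference.
- **Exclusion Criteria, item 5:** removes patients who leave against advice or are "otherwise removed from the medical system before their work up has been completed".
- **Introductory text before Rationale:** fluid in any standard FAST view sends the patient to the operating room. No equivalent route is described for a subject positive on FASTeR alone or negative on both exams.
- **Rationale:** FASTeR is done when appropriate, so it may be missing in some enrolled subjects.
- **Study Duration:** accrual is raised from 209 to 250 for subjects meeting exclusion criteria, not for a missing reference.

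No section gives an expected verification rate, a follow-up standard for subjects without CT or surgery, a missing-data method, or a correction for verification bias.

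**The concern.** In a diagnostic accuracy study, the 2x2 table is unbiased only if having the reference result does not depend on the index-test result. Here a positive FAST leads to an operation, which supplies the reference. A subject negative on both exams receives it only if routine care calls for it, and the complete-case rule removes the subject otherwise. Removing double-negatives with hemoperitoneum shrinks the denominator of both sensitivities. Removing double-negatives without it shrinks the denominator of both specificities while leaving the false positives in place.

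These estimates are the primary results. Predictive values, false-negative rates and likelihood ratios come from the same table.

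**Working it through.** **Inputs from the plan (Study Duration).** FAST detects up to 60% of diseased subjects, and FASTeR detects 1 in 4 of those whom FAST misses.

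- Positive on either exam: 0.60 + 0.25 × 0.40 = 0.70.
- Negative on both: 0.75 × 0.40 = 0.30.
- The 0.70 is FASTeR's own sensitivity only if every FAST-positive diseased subject is also FASTeR-positive (nested results). That is assumed below.

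**The plan's sample size.** A one-sample, one-sided 5% test of 0.60 against 0.70 at 90% power gives (1.645 + 1.282)² × 0.24 / 0.10² ≈ 206, close to the stated 209. The figure does not bear on the bias.

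**Assumed inputs.** Verification rates are not in the documents, so a range is used. True specificity is taken as 97% for FAST and 95% for FASTeR; the protocol quotes 94.7–99.6% for FAST.

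**A. Only double-negatives are incompletely verified, at rate v.**

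Apparent sensitivity = s / (0.70 + 0.30v). Apparent specificity = 1 − FP / (0.05 + 0.95v), where FP is 0.03 or 0.05.

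| v | Sensitivity denominator | Sensitivity, FAST v FASTeR | Difference (points) | Specificity, FAST v FASTeR |
|---|---|---|---|---|
| 1.0 | 1.00 | 60.0% v 70.0% | 10.0 | 97.0% v 95.0% |
| 0.9 | 0.97 | 61.9% v 72.2% | 10.3 | 96.7% v 94.5% |
| 0.7 | 0.91 | 65.9% v 76.9% | 11.0 | 95.8% v 93.0% |
| 0.5 | 0.85 | 70.6% v 82.4% | 11.8 | 94.3% v 90.5% |

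The sensitivity ratio stays at 0.70/0.60 = 1.17. McNemar's discordant counts are also unchanged, because double-negatives are concordant.

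**B. FASTeR-only positives are also incompletely verified.** Only a positive standard FAST is documented as leading to surgery.

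- Both groups at 70%: denominator 0.60 + 0.07 + 0.21 = 0.88. FAST is 0.60/0.88 = 68.2% and FASTeR is 0.67/0.88 = 76.1%. The difference is 8.0 points and the ratio 1.12.
- Both at 50%: denominator 0.60 + 0.05 + 0.15 = 0.80. FAST is 75.0% and FASTeR is 0.65/0.80 = 81.3%. The ratio is 1.08.

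The levels are still inflated, but the advantage of FASTeR is understated, and discordant pairs are lost from McNemar's test.

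**C. FAST-positive subjects are operated on before a FASTeR and dropped as incomplete.**

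- 20% of them lost, all others kept: denominator 0.48 + 0.10 + 0.30 = 0.88. FAST is 0.48/0.88 = 54.5% and FASTeR is 0.58/0.88 = 65.9%. Both are understated, and the ratio is 1.21.
- 20% of them and 20% of double-negatives lost: denominator 0.48 + 0.10 + 0.24 = 0.82. FAST is 58.5% (understated) and FASTeR 70.7% (slightly overstated).

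**D. What a correction and bounds would give.** Assume 250 subjects, 30% with hemoperitoneum (75 v 175), FASTeR 70% sensitive and 95% specific, and v = 0.5 regardless of disease.

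- Complete case: 52.5 / (52.5 + 11.25) = 82.4%.
- Inverse-verification (Begg-Greenes) estimate: 52.5 / (52.5 + 11.25/0.5) = 70.0%, the true value.
- Unverified subjects: 0.5 × (22.5 + 166.25) = 94.4. If none is diseased, sensitivity is 82.4%. If all are, it is 52.5 / (63.75 + 94.4) = 33.2%.

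**The case against.** The strongest reply is that verification may be nearly complete. Rationale says that exam results will be confirmed by CT or operation. Research Design lists a CT- or operation-confirmed injury complex among the data for each enrolled subject. The inclusion criterion requires hemodynamic instability with suspected blunt abdominal injury, and diseased double-negatives may show signs that prompt imaging. If 95% of them are verified, the denominator is 0.70 + 0.285 = 0.985 and the sensitivities read 60.9% v 71.1%, a trivial shift.

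This stands as a limit on the size. It does not remove the gap: a list of requested data does not ensure that every subject is verified, the reference fields are qualified on the form, and a subject without the field fails the complete-data rule. The other-imaging line does not settle it either, because the analysis section recognises only CT or operative findings.

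A reader might infer that double-negatives do drop out and that both sensitivities, and their difference, are overstated. The documents do not support that. They nowhere say that double-negatives go unverified, they give no rate, and scenarios B and C show that the same rule can shrink the difference or understate both exams. Nor do they show that exclusion 5 depends on scan results: it is a stated eligibility criterion, and the protocol does not say whether those patients had been scanned.

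**Conclusion.** The concern holds as a risk of unknown size and direction. Complete-case analysis with a reference obtained only through routine care lets entry to the 2x2 table depend on the scan results, and the plan neither measures nor bounds the effect on its primary estimates.

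If mainly double-negatives are unverified, sensitivity is inflated by about 2 points at 90% verification and by 11 to 12 points at 50%, and specificity is deflated. This rests on the plan's 60% and 70%, nested results, full verification of everyone positive on either exam, and an assumed rate. The sensitivity ratio and McNemar's test are protected only under that full-verification condition and if no FAST-positive subject is dropped for want of a FASTeR.

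**What to change.** Amend the Statistical Analysis Plan as follows.

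1. Keep every enrolled and scanned subject in the analysis database, with or without a reference result.
2. Report the number with a CT or operative reference in each FAST-by-FASTeR result pattern, including a row for FASTeR not done.
3. Beside the complete-case estimates, give a verification-bias-corrected estimate, for example Begg-Greenes or inverse probability of verification, with bounds that treat all and then none of the unverified subjects as diseased.
4. Report relative true-positive and false-positive rates, stating that they are robust to missing verification only if everyone positive on either exam is verified.
5. In the sensitivity analysis, count subjects who were scanned but left before work-up was complete as unverified, where their data were collected.

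No patient's care changes. The verification method is already on the form (Study Outcome Measures, item 6), so most of the cost is a little extra analysis; sites must also submit records that lack a reference result. The correction assumes that verification depends only on the recorded scan results, which is why the bounds are needed, and they can be wide, as step D shows. The rule should be set in advance: satellite data arrive de-identified, and Confidentiality and Privacy has the code list and study data destroyed after completion, so records not retained may be unrecoverable.
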